13.2.1.3 Monitoring

For a possible Hy's Law case (ALT \geq 3x ULN AND total bilirubin \geq 2x ULN or INR $>$ 1.5):

- Repeat liver chemistry tests (include ALT, AST, ALP, GGT, bilirubin, total bile acids, PT/INR, and PTT) and perform liver event follow-up assessments within **24 hours**.
- Collect blood samples twice weekly for repeat liver chemistry tests (ALT, AST, ALP, GGT, bilirubin, total bile acids, PT/INR, and PTT) until abnormalities resolve, stabilize, or return to baseline.
- A specialist or hepatology consultation is recommended.

For a non-Hy's Law case of ALT \geq 3x ULN that meets other liver chemistry stopping criteria:

- Repeat liver chemistry tests (include ALT, AST, ALP, GGT, bilirubin, total bile acids, PT/INR, and PTT) and perform liver event follow-up assessments within 24 to 72 hours.
- Collect blood samples weekly for repeat liver chemistry tests (ALT, AST, ALP, GGT, bilirubin, total bile acids, PT/INR, and PTT) until abnormalities resolve, stabilize, or return to baseline.

13.2.2 Increased Liver Chemistry Monitoring While Continuing Study Drug

If ALT \geq 3x ULN and $<$ 5x ULN **and** total bilirubin $<$ 2x ULN, **without** symptoms believed to be related to liver injury or hypersensitivity, **and** the subject can be monitored weekly for 4 weeks, perform the following actions:

- Notify the Medical Monitor within **24 hours** of learning of the abnormality to discuss subject safety.
- Subject can continue study drug.

- Collect blood samples weekly for repeat liver chemistry tests (ALT, AST, ALP, GGT, bilirubin, total bile acids, PT/INR, and PTT) until the abnormalities resolve, stabilize, or return to baseline.
- If at any time the subject meets liver chemistry stopping criteria, proceed as described in [Section 7.1.1](#) and [Section 13.2.1](#).
- If, after 4 weeks of monitoring, ALT <3x ULN and total bilirubin <2x ULN, monitor per standard scheduling for remainder of study and follow-up period.

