7.1.1 Liver Chemistry Stopping Criteria

Liver chemistry stopping criteria defined in [Table 3](#) are designed to ensure subject safety and to evaluate liver event etiology. The Investigator should notify the Sponsor within 24 hours of awareness if any of the criteria defined in [Table 3](#) are met. Further suggested actions, follow-up assessments, and monitoring assessments are provided in [Section 13.2](#). A significant change in liver chemistry that requires increased monitoring but does not necessarily satisfy stopping criteria may still be considered an adverse event of special interest (AESI) (see [Section 8.3.8](#)).

Table 3. Stopping Criteria and Increased Monitoring for Liver Chemistry Elevations

Criteria	Actions	
ALT \geq 5x ULN	Discontinue study drug and notify Sponsor.	
ALT \geq 3x ULN	AND total bilirubin \geq 2x ULN (>35% direct bilirubin) ¹	Discontinue study drug and notify Sponsor. Possible Hy's Law case— report as SAE .
	AND INR >1.5	Discontinue study drug and notify Sponsor. Possible Hy's Law case— report as SAE .
	AND subject has symptoms (new or worsening) believed to be related to liver injury or hypersensitivity ²	Discontinue study drug and notify Sponsor.
	AND total bile acids >3x ULN	Withhold study drug and notify Sponsor. Repeat liver chemistry tests after 1 week, and discuss with Medical Monitor whether to discontinue study drug.
	ALT \geq 3x ULN only	Monitor weekly for 4 weeks while continuing study drug and notify Sponsor (see Section 13.2.2)
	AND cannot be monitored weekly for 4 weeks	Discontinue study drug and notify Sponsor.
	persists for \geq 4 weeks	Discontinue study drug and notify Sponsor.

Abbreviations: ALT, alanine aminotransferase; INR, international normalized ratio; SAE, serious adverse event; ULN, upper limit of normal.

¹ If serum bilirubin fractionation is not immediately available, discontinue study drug if ALT \geq 3x ULN and bilirubin \geq 2x ULN and record the presence/absence of detectable urinary bilirubin on dipstick, which is indicative of direct bilirubin elevations suggesting liver injury.

² Symptoms related to liver injury include fatigue, nausea, vomiting, right upper quadrant pain or tenderness, and jaundice. Symptoms related to hypersensitivity include fever, rash, and eosinophilia.

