13.2.1.1 Actions

- Immediately discontinue study drug.
- Within 24 hours, report the event to the Sponsor or designated CRO and complete the AE eCRF (indicating that it is an AESI).
- If the event also meets the criteria for an SAE (see [Table 3](#)), complete the SAE fields in the eCRF.
- Request list of any medications taken in last 48 hours. Specifically question about medications that are known to increase liver enzymes, such as aspirin, acetaminophen, ibuprofen, naproxen, diclofenac, phenylbutazone, and any antibiotics.
- Perform liver chemistry follow-up assessments (see [Section 13.2.1.2](#)).
- Monitor the participant until liver chemistry test abnormalities resolve, stabilize, or return to baseline (see [Section 13.2.1.3](#)).
- If restart/rechallenge is not granted, permanently discontinue study drug and continue participant in the study for any protocol-specified follow-up assessments.

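### At ALT 3 to <5x ULN with total bile acids >3x ULN, Protocol 13.2.2, Table 3 and 13.2.1.1 can be read as continue, withhold or discontinue study drug

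*Protocol*

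**What the plan says.** Three places in the protocol govern this situation.

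- **Section 13.2.2.** The entry list covers ALT (at least 3x and below 5x ULN), total bilirubin (below 2x ULN), absence of liver or hypersensitivity symptoms, and feasibility: "the subject can be monitored weekly for 4 weeks, perform the following actions". The actions include notifying the Medical Monitor within 24 hours, then "Subject can continue study drug", then weekly tests: "Collect blood samples weekly for repeat liver chemistry tests (ALT, AST, ALP, GGT, bilirubin, total bile acids, PT/INR, and PTT". An override follows: "If at any time the subject meets liver chemistry stopping criteria, proceed as described in" Sections 7.1.1 and 13.2.1. The closing bullet also rests on ALT and bilirubin alone: "If, after 4 weeks of monitoring, ALT <3x ULN and total bilirubin <2x ULN, monitor per standard scheduling".
- **Section 7.1.1, Table 3.** At ALT at least 3x ULN with total bile acids above 3x ULN the action is "Withhold study drug and notify Sponsor", with repeat tests after 1 week and a discussion with the Medical Monitor about discontinuing. INR above 1.5 at the same ALT is a discontinue row. Only the row for an isolated ALT elevation refers the reader to 13.2.2.
- **Section 13.2.1.1.** For subjects who meet stopping criteria the first action is "Immediately discontinue study drug".

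**The concern.** The 13.2.2 list reads as complete. It repeats the bilirubin, symptom and monitoring limits that Table 3 already carries, but not the bile-acid limit. A site that opens the appendix with a laboratory report in hand can tick every condition for continuing while Table 3 tells it to withhold.

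Liver safety is where this matters most. Section 2.3.3 cites strict liver stopping criteria as part of the mitigation of risk, and Section 5 plans approximately 130 sites, so different readings are plausible. The bile-acid and ALT combination is not incidental either: SAP Table 10 flags bile acids above 3x ULN when ALT is above 3x ULN.

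There is a reporting consequence as well. SAP 14.1.2 tabulates TEAEs leading to study drug discontinuation, and SAP 13.3.5.1 defines retrieved dropouts by premature discontinuation. Whether the same report is handled as continued treatment, an interruption or a discontinuation changes who enters those counts.

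**Working it through.** No sample-size or error-rate figure is involved, so the check is a comparison of rules.

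**Step 1: grid.** Take asymptomatic subjects who can be monitored weekly, with ALT 3, 4 or 4.9x ULN, bilirubin 1.0 or 1.9x ULN, INR 1.0 or 1.6, and bile acids 1 or 3.1x ULN. That gives 3 × 2 × 2 × 2 = 24 cases. All 24 satisfy the 13.2.2 entry list. Each INR and bile-acid combination holds 3 × 2 = 6 cases.

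| INR >1.5 | Bile acids >3x ULN | Cases | Table 3 action |
|---|---|---|---|
| no | no | 6 | continue, weekly monitoring |
| no | yes | 6 | withhold |
| yes | no | 6 | discontinue |
| yes | yes | 6 | discontinue row and withhold row both met |

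These counts show where the rules differ. They do not estimate how often it would happen.

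**Step 2: apply the override.** INR above 1.5 is a discontinue row, so it is a stopping criterion on any reading. The override sends those 6 + 6 = 12 cases back to Table 3 and 13.2.1, and the disagreement goes. The 6 cases with raised bile acids only remain.

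**Step 3: the remaining cases.** The outcome turns on whether the withhold row is a stopping criterion.

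- *If it is not*, the override is not triggered. Section 13.2.2 allows drug to continue; Table 3 withholds it.
- *If it is*, the override points to two places at once. Table 3 says withhold, retest at 1 week, then discuss; 13.2.1.1 says discontinue immediately.

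**Step 4: does the text settle the status of the row?** Section 7.1.1 says that the stopping criteria are those in Table 3. But the table's title covers both stopping criteria and increased monitoring, and one of its rows keeps the subject on drug. So not every row can be a stopping criterion, and the table does not mark which ones are.

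**Step 5: example.** ALT 4x, bilirubin 1x, bile acids 4x ULN, no symptoms, weekly monitoring possible. Section 13.2.2: may continue. Table 3: withhold. Section 13.2.1.1, if reached: discontinue.

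**The case against.** The best defence is that the protocol should be read as a whole. Table 3 refers to 13.2.2 only from the isolated-ALT row, so a subject with raised bile acids is never sent there. Section 13.2 opens by pointing to 7.1.1 for the stopping criteria. The heading of 13.2.1 and the text of 7.1.1 both call the appendix actions suggested, so a specific Table 3 row should prevail. Continuing under 13.2.2 is permissive and comes with Medical Monitor notification within 24 hours. Section 13.2.1.1 also mentions permanent discontinuation as a later step, which narrows the gap between withholding and discontinuing.

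Much of this stands, and a careful reader who starts at Table 3 will probably withhold. But the limiting word in the Table 3 row does not appear in 13.2.2, no sentence says that Table 3 prevails, and notifying the Medical Monitor does not say which passage governs. The routes back to treatment differ too. Table 3 describes a 1-week repeat and a discussion. If the row counts as a stopping criterion, Section 13.2.3 could apply, with its clear underlying cause, exclusion of drug-induced injury, written Sponsor approval and twice-weekly draws.

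A reader might infer two stronger points, and the documents support neither. The first is that 13.2.2 keeps subjects on drug without checking bile acids or INR. Both are in its weekly test panel; what is missing is their use as a condition. The second is that INR above 1.5 is also left in conflict. The entry list does omit it, but the override in the same section resolves it.

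**Conclusion.** The point holds as an unresolved inconsistency over one Table 3 row. For ALT at least 3x and below 5x ULN with bile acids above 3x ULN and the other 13.2.2 conditions met, the three passages can be read as continue, withhold or discontinue, and the protocol does not say how the withhold row is classed. This rests on the wording alone and assumes INR is not above 1.5. The number of subjects affected cannot be derived, and nothing here shows that any subject would be mismanaged. The primary analysis is not threatened in principle, because SAP 13.3.1 uses A4 data regardless of treatment interruption or discontinuation. The stake is consistent liver-safety conduct across sites and consistent coding of discontinuations.

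**What to change.** Reconcile Table 3 (Section 7.1.1), Section 13.2.1.1 and Section 13.2.2:

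- Make the 13.2.2 entry conditions and the isolated-ALT row of Table 3 describe the same set of subjects, and check the return-to-schedule bullet for the same gap. Completing the list for INR at the same time would be tidy, though the override already covers it.
- State whether the bile-acid withhold row is a stopping criterion for 13.2.1 and 13.2.2, and hence whether 13.2.3 applies to resuming drug.
- Say which passage governs if they differ.

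Which clinical action applies is for the sponsor's clinical team. The cost is protocol wording and informing sites; no design, sample-size or analysis change follows.

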13.2.3 Restart Following Transient Resolving Liver Chemistry Events Not Related to Study Drug

The Investigator may request the Sponsor to consider restarting study drug in a subject who stopped study drug because of a liver chemistry event. Approval for study drug restart can be considered under the following circumstances:

- Liver chemistry events have a clear underlying cause (eg, biliary obstruction, pancreatic events, hypotension, acute viral hepatitis), liver chemistry tests have improved to normal or are within 1.5x baseline, and ALT <3x ULN.
- Possible drug-induced liver injury (DILI) has been excluded by the Investigator and the study team. This includes the absence of markers of hypersensitivity (otherwise unexplained fever, rash, eosinophilia). Where a study medication has an identified genetic marker associated with liver injury (eg, lapatinib, abacavir, amoxicillin/clavulanate), the presence of the marker should be excluded. If study drug-related liver injury cannot be excluded, the guidance on appropriate action and follow-up in the previous sections of this Appendix will apply.
- There is no evidence of alcoholic hepatitis.
- Medical Monitor approval of study drug restart has been obtained.

If restart of study drug is approved by the Sponsor in writing:

- Study drug must be administered at the dose specified by the Sponsor.
- Subjects approved by the Sponsor for restart of study drug must have twice weekly blood draws for liver chemistry tests until stable liver chemistry tests have been demonstrated, and then standard laboratory monitoring may resume as per protocol.
- If the subject meets protocol-defined liver chemistry stopping criteria after study drug restart, study drug should be permanently discontinued.
- The Medical Monitor must be informed of the outcome for the subject following study drug restart.
- The Sponsor must be notified of any AEs.

13.3 Appendix of Clinical Laboratory and Urinalysis Tests

Refer to [Section 8.2.5](#) for more information on clinical laboratory and urinalysis tests.

Laboratory Assessments	Parameters	
Hematology	Platelet count	
	RBC count	
	RBC indices: MCV, MCH, % reticulocytes	
	Hemoglobin	
	Hematocrit	
WBC count		
	Differential: neutrophils, lymphocytes, monocytes, eosinophils, basophils	
Clinical Chemistry ¹	Potassium	ALP
	Calcium	ALT/SGPT
	Sodium	AST/SGOT
	BUN	GGT
	Creatinine	Total and direct bilirubin
	Total protein	Total bile acids
Coagulation	PT/INR, PTT	
Lipid Panel	Total cholesterol, LDL, HDL, triglycerides	
Thyroid Panel	T3 (free and total), T4 (free and total), TSH	
Routine Urinalysis	Specific gravity pH, glucose, protein, blood, ketones, bilirubin, urobilinogen, nitrite, by dipstick Microscopic examination (if blood or protein is abnormal)	
Other Tests	LH, FSH, SHBG, renin, aldosterone	
	For males only: inhibin B	
	For females only: estradiol, prolactin, progesterone	

Abbreviations: ALP, alkaline phosphatase; ALT, alanine aminotransferase; AST, aspartate aminotransferase; BUN, blood urea nitrogen; FSH, follicle-stimulating hormone; GGT, gamma-glutamyl transferase; HDL, high-density lipoprotein; INR, international normalized ratio; LDL, low-density lipoprotein; LH, luteinizing hormone; MCH, mean corpuscular hemoglobin; MCV, mean corpuscular volume; PT, prothrombin time; PTT, partial thromboplastin time; RBC, red blood cell; SAE, serious adverse event; SGOT, serum glutamic-oxaloacetic transaminase; SGPT, serum glutamic-pyruvic transaminase; SHBG, sex hormone-binding globulin; TSH, thyroid-stimulating hormone; ULN, upper limit of normal; WBC, white blood cell.

¹ Details of liver chemistry stopping criteria and required actions and follow-up assessments after liver stopping or monitoring event are given in [Section 7.1.1](#) and [Section 13.2](#). All events of ALT ≥ 3 x ULN plus total bilirubin ≥ 2 x ULN ($>35\%$ direct bilirubin) or ALT ≥ 3 x ULN plus INR >1.5 may indicate severe liver injury (possible Hy's Law) and must be reported as SAEs.

13.4 Appendix Regarding Genetic Sample Collection and Testing

Where local regulations permit and subject to discretionary approval from each site's IRB/EC and to subject consent, a voluntary blood sample may be collected for DNA analysis. These samples may be tested for CAH genotype, genes related to the mechanism of action of tildacerfont, and drug metabolism enzyme and transporter polymorphisms. Drug metabolism enzyme and transporter polymorphisms may be evaluated using an analytical methodology that comprehensively assesses an array of drug metabolism enzyme and transporter genes from a single sample. Alternative genotyping platforms may be used, if appropriate, to confirm initial results. Certain genotyping may be omitted at the discretion of the Investigator and/or Sponsor (eg, if the subject was previously tested for certain genes using the same platform/technology). No additional testing will be performed on these samples.

Details regarding the collection, processing, storage, and shipping of samples can be found in the Laboratory Manual. Samples collected as part of a later analysis will be securely stored in a central biorepository selected by the Sponsor for up to 5 years after the last study visit of the last subject in the study, or as local regulations allow. Any samples remaining after 5 years will be destroyed.

---

## List of Abbreviations and Definition of Terms

Abbreviation	Description
17-OHP	17-hydroxyprogesterone
A4	androstenedione
ACTH	adrenocorticotropic hormone, corticotropin
ADAM	analysis data model
AE	adverse event
AESI	adverse event of special interest
AIC	Akaike information criterion
BID	Twice daily
BLQ	Below level of quantification
BMI	body mass index
BP	blood pressure
C-SSRS	Columbia–Suicide Severity Rating Scale
CAH	congenital adrenal hyperplasia
CGI-I	Clinical Global Impression – Improvement Scale
CI	confidence interval
CFB	change from baseline
CRF	corticotropin-releasing factor
CRO	contract research organization
CSR	clinical study report
CTCAE	Common Terminology Criteria for Adverse Events
CV	coefficient of variation
ECG	electrocardiogram
eCRF	electronic case report form
GC	glucocorticoid
GM	geometric mean
GMR	geometric mean ratio
HADS	Hospital Anxiety and Depression Scale
HbA1c	hemoglobin A1c
HC	hydrocortisone
HCe	hydrocortisone equivalent(s)
HDL	high-density lipoprotein
HOMA-IR	homeostatic model assessment of insulin resistance
HR	heart rate
IGA	Investigator's Global Assessment (of acne severity)
ITT	Intent to Treat (Population)

Abbreviation	Description
LDL	low-density lipoprotein
LFT	liver function test
log	logarithmic function
LS	least squares
MCP-Mod	Multiple Comparison Procedure – Modelling
MedDRA	Medical Dictionary for Regulatory Activities
MDRI	Multi Domain Response Index
mFG	modified Ferriman Gallwey (score for hirsutism)
mITT	modified Intent to Treat (Population)
MMRM	mixed-model for repeated measures
PCSA	potentially clinically significant abnormality(ies)
PGIC	Patient Global Impression of Change
PK	pharmacokinetic
PP	per-protocol
PT	preferred term
QD	once daily
QoL	quality of life
QTcF	Fridericia-corrected QT interval
REML	restricted maximum likelihood
RTSM	randomization and trial supply management
SAE	serious adverse event
SAP	statistical analysis plan
SF-36	Short Form 36
SOC	system organ class
TART	testicular adrenal rest tumor
TEAE	treatment-emergent adverse event
ULN	upper limit of normal
WHO DD	World Health Organization Drug dictionary

## 1 REVISION HISTORY

Version	Date	Document Owner	Revision Summary
1.0	31 December 2023	[name]	First version

## 2 RELATED DOCUMENTS: PROTOCOL AND CASE REPORT FORMS

Version	Date
Protocol Version 1.0	19DEC2019
Protocol Version 2.0	30JAN2020
Protocol Version 3.0	14FEB2020
Protocol Version 4.0	14APR2020
Protocol Version 5.0	31AUG2020
Protocol Version 6.0	31MAR2021
Protocol Version 7.0	14MAR2022
Case Report Forms	02JAN2023

## 3 COMMITMENT TO GOOD STATISTICAL PRACTICE

### 3.1 Definition of Good Statistical Practice

The International Council for Harmonisation Guideline on Statistical Principles for Clinical Trials (ICH E9) implicitly defines good statistical practice. Good statistical practice includes both appropriate statistical designs to minimize bias and maximize precision of analysis plus operational excellence to assure credibility of results. The scientific design associated with any clinical trial is found in the protocol. More detailed, pre-specified statistical analysis methods can be found in the statistical analysis plan.

We interpret the operational side of good statistical practice as a transparent, reproducible, and validated approach to acquiring and analyzing clinical trial data. Reproducible research depends upon process transparency and also provides auditability of the statistical analysis. Analysis transparency requires that a navigable electronic process chain exists from defining the objective of the analysis to creating the results.

### 3.2 Use of Standards

Data standards are foundational for creating an environment where tools can be leveraged at different points in the analysis process. Data standards for clinical development of drugs have been defined and are maturing under various initiatives through the Clinical Data Interchange Standards Consortium (CDISC). Spruce Biosciences uses standard data tabulation model (SDTM) data sets and Analysis Data Model (ADaM) statistical analysis files for producing analysis results. Other applicable standards include regulatory guidance from the Food and Drug Administration (FDA) and ICH:

- ICH Guideline on the Structure and Content of Clinical Study Reports (ICH E3)
- ICH Guideline for Good Clinical Practice (ICH E6)

## 4 PURPOSE OF THE ANALYSIS PLAN

This statistical analysis plan (SAP) pre-specifies the statistical analysis methods for supporting the completion of the clinical study report (CSR) of Study SPR001-203 for investigational product SPR001 (referred to as tildacerfont hereafter), an investigational drug candidate designed to treat classic congenital adrenal hyperplasia (CAH). This SAP will be used to analyze the primary efficacy, final efficacy, and safety data collected during the study. The analysis of the open label extension period will be covered in a separate SAP. Dose-exposure-response analyses combining data across multiple studies will be conducted using a separate pharmacokinetics SAP. The planned analyses identified in this SAP may be included in regulatory submissions and/or future manuscripts.

The analysis methods described in this plan are considered *a priori*, in that they have been defined prior to clinical database lock and treatment unblinding. Exploratory analyses that are not defined in this SAP, may be performed to support the clinical development program. Any post-hoc or unplanned analyses that are performed for the CSR, but not defined in this SAP, will be documented in the CSR. Changes from the planned analyses stated in the study protocol are described in [Section 15](#). Should the SAP and the protocol be inconsistent with respect to any further planned analyses, the language of the SAP is governing.

The analysis of pharmacokinetic (PK) concentration data and its parameters, as well as the analysis of the optional open-label extension period will be captured in separate SAPs.

